11.2 Intent-to-Treat Participant Population

The intent-to-treat population is defined as the participants who are randomized to treatment.

11.3 Analysis Plan

Each primary and secondary efficacy outcome measure will be analyzed for the intent-to-treat (ITT) population. While there is every intention to be complete in describing the analyses to be performed, it is not possible to anticipate every contingency, and some adjustments may be required to meet constraints posed by the structure of the data. Constraints such as non-linearity, non-normality, etc. may lead to different but more appropriate approaches to analysis.

All statistical tests will be conducted at the 5% Type I error rate (two-sided). When multiple tests are conducted, the chance of finding a significant difference in one of the tests, when in fact no difference exists, is greater than the stated Type I error rate. The investigators are aware of the multiple testing issues and will interpret results with caution and use confidence intervals where possible.

11.3.1 Primary Outcome

The primary hypothesis is that a significantly greater percentage of TAU+SCT, relative to TAU, participants will be stimulant-free during the weeks of the active treatment phase. For each participant, a stimulant-free week is defined as a week in which both urine samples test negative for stimulants and the participant self-reports no illicit stimulant use. A stimulant-positive week is defined as a week in which at least one urine sample tests positive for a stimulant or during which the participant self-reports illicit stimulant use. However, in the analysis of data from any clinical trial, strategies must be employed for handling missing data. In this trial, data for a week in which both urine samples are missing and the participant self-reports no illicit stimulant use will be treated as missing. For a week in which one stimulant-free UDS is produced, the second urine sample is missing, and the participant self-reports no illicit stimulant use or the self-report data are missing will be treated as negative (Table 6).

Data will be analyzed using a generalized linear mixed model (GLMM) for repeated-measures analysis (Brown and Prescott, 1999). Suppose Y represents the vector of observed response data, X and Z the fixed and random effects design matrices, and α and β be the vectors of fixed and random effects, respectively. Then, the GLMM model formulation assumes that

$$\mathrm{E}(\mathrm{Y}|\beta) = g^{-1}(\mathrm{X}\alpha + \mathrm{Z}\beta),$$

where $E(Y|\beta)$ is the expected value of Y conditional on the random effects vector, g^{-1} is the inverse link function, and $X\alpha + Z\beta$ is the linear predictor. The response variable Y will be modeled using the logit link function, i.e., $g(\mu) = \log(\mu / (1 - \mu))$. Fixed effects will include treatment group and week, while random effects will include site. SAS Proc GLIMMIX will be used to fit the model as follows:

proc glimmix; class site treatment; model Y = treatment week treatment*week / dist=binary link=logit covb solution; random intercept / subject=site; random _*residual_*/subject=patientid type=cs; run;

The model formulation implies the same treatment effect in each site. The effect of the intervention on change in response from baseline will be addressed by the treatment by week interaction parameter. Due to the possibility that CTPs may differ in their success at helping participants become/remain stimulant-free, each regression model will adjust for site effects. Site will be included in the GLMM model as a random effect based on the participation of 12 CTPs. Assumptions of linearity will be examined by adding a restricted cubic spline to represent nonlinearity (Harrell, 2001). Assumptions for the covariance structure that provides the best fit to the data will be analyzed using the COVTEST statement under SAS Proc GLIMMIX. Since GLMM inference is only valid if data are missing at random (MAR), logistic regression analyses will be conducted to identify patterns of attrition and to determine if there is differential attrition by treatment condition. A binary indicator variable for missing data will be regressed on treatment assignment and other covariates. Variables that are associated with attrition at or below the α =0.10 level of significance will be included in subsequent analyses where the assumption of data missing at random (conditional on covariates) is required (Verbeke and Molenberghs, 2000).

If the random effects model unexpectedly fails to converge, then a general estimating equation (GEE) approach will be employed treating site as a fixed effect. If this model is utilized, then missing data (see Table 6) will be imputed using standard multiple imputation procedures, since GEE inference is only valid if data are missing completely at random (MCAR). SAS Proc MI will be used to create five complete data sets

using multiple imputation. Each data set subsequently be analyzed using SAS Proc GENMOD (the GEE procedure), and the results combined using SAS Proc MIANALYZE.

Urine Drug Screen - Stimulant result		Time Line Follow Back (TLFB)				
Result	Result	At least one positive day	All days negative	Some days negative, some missing	All days missing	
-	-	+	-	-	-	
+	-	+	+	+	+	
+	+	+	+	+	+	
+	0	+	+	+	+	
0	0	+	Missing	Missing	Missing	
_	0	+	-	-	-	

Table 6:	Stimulant-	use assignment	t for study	week as a	a function	of TLFB and	UDS result
			•				

Note: '0'=missing, '+'=positive and '-'=negative

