6.5 Outcome Measures

6.5.1 Primary Outcome Measure – Stimulant-free Weeks

The primary outcome measure is whether (yes/no) a participant is stimulant-free during each week of the active treatment phase, as assessed by qualitative urine drug screen (UDS). At the group level, this outcome translates into the percentage of participants in each study arm who are stimulant-free during each week of the active treatment phase. This outcome was selected as primary since it is an objective measure of a critical stimulant-dependence outcome: stimulant use. During the active treatment phase, participants ideally will be scheduled to provide two urine samples per week on nonconsecutive days. A rapid UDS system that screens for drugs of abuse including cocaine, methamphetamine, amphetamine, opioids, benzodiazepines, and marijuana will be used to analyze the urine samples. Urine samples will be collected using temperature monitoring and the validity of urine samples will be checked with the use of a commercially available adulterant test. In cases where the temperature reading/adulterant test indicates a non-valid sample, an attempt will be made to obtain a second urine sample. The strategies that will be employed for handing missing data are outlined in section 11.3.1.

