8.0 STUDY MEDICATIONS

8.1 Bupropion XL

Bupropion hydrochloride XL 150 mg (for dose escalation and taper) and 300 mg tablets, manufactured by GlaxoSmithKline, will be used in the present trial. Bupropion hydrochloride powder is white, crystalline, and highly soluble in water. The structure of bupropion XL closely resembles that of diethylpropion and it is related to phenylethylamines. Its molecular formula is $C_{13}H_{18}$ CINO•HCl and its molecular weight is 276.2.

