11.4 Sample Size Estimate

The minimum sample size required to achieve 80% power using an alpha level of 0.05 (two-sided) and a 1:1 randomization ratio was computed based on a repeated measures study design that takes into account that the data are binary and can be correlated across repeated measurements (Rochon, 1998). We assumed a compound symmetry covariance structure to be conservative (correlation between 2 successive time points does not change over time), as well as a maximum correlation between any 2 time points of 0.65. The higher the assumed correlation between time points, referred to as phi, the less information that we gain from successive measurements, thus requiring a larger sample size. The assumption of 0.65 for the present study is based on the phi calculated for the stimulant UDS results from the subgroup of cocaine dependent participants in CTN-0009, a study that evaluated the impact of concurrently providing smoking-cessation treatment with substance-abuse treatment.

The probability of stimulant-free urines in the TAU group is another key assumption in determining sample size. A review of the stimulant UDS results for cocaine-dependent participants from three prior CTN studies, CTN-0009, CTN-0015 (Seeking Safety for women with PTSD and substance-use disorders), and CTN-0006 (Contingency management for stimulant abusers) produced probabilities ranging from 0.55 to 0.75, with the lower probabilities (i.e., 0.55) requiring larger sample sizes. Based on these prior studies, we assumed a probability of 0.6 for stimulant-free urines in the TAU group. A final key consideration in calculating sample size is the size of the group difference to be detected. The present study has been powered to detect the lower limit of a clinically meaningful effect. Specifically, this study will detect a group difference if the probability of stimulant-free urines in the TAU+SCT group is at least 0.7.

The sample size yielded from the assumptions outlined above is 528, with 264 in each treatment group. As described in section 11.6, an interim analysis to evaluate the accuracy of the assumptions made in calculating this sample size will be conducted, with an adjustment made to the sample size if needed.

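### If the rapid urine screen cross-reacts with bupropion, the fixed week-scoring rule would put the false positives mainly in TAU+SCT, and the plan has no scoring that would show it

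*Protocol*

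**What the plan says.** - **Assay.** Protocol 6.5.1: "A rapid UDS system that screens for drugs of abuse including cocaine, methamphetamine, amphetamine, opioids, benzodiazepines, and marijuana will be used". The specimen checks described are temperature and an adulterant test. No confirmatory assay is described.
- **Scoring.** Protocol 11.3.1: "A stimulant-positive week is defined as a week in which at least one urine sample tests positive for a stimulant". In Table 6 one positive urine gives a positive week in every self-report column, including the one where all days are negative. The limitation to illicit use attaches to the self-report part of the rule, not to the urine part. No list says which strips count as a stimulant.
- **Exposure.** All TAU+SCT participants are to receive bupropion XL through the 10-week active phase (7.4, 8.10.1). TAU receives none from the study, and there is no placebo. TAU participants may seek outside smoking treatment, which is recorded (6.7.2).
- **Chemistry.** Protocol 8.1: "The structure of bupropion XL closely resembles that of diethylpropion and it is related to phenylethylamines". The protocol does not relate this to the urine screen.
- **Baseline.** Use of bupropion within 14 days of randomization is an exclusion (6.4.2.2, criterion 11).

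**The concern.** The protocol's own description of the study drug raises the question of whether the drug could produce a positive amphetamine result. If it could, the error would not be spread evenly. It would fall mainly on the arm that is given the drug, and it would lower that arm's stimulant-free rate. The rule offers no way back: a negative self-report cannot reverse a positive urine, and a positive on the amphetamine strip alone is not treated separately. Baseline urines cannot reveal the problem, because recent bupropion users are excluded, and stratifying on the baseline urine result does not protect against it.

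The trial is meant to tell apart benefit, harm and no effect on stimulant use (section 3.0). An error of this kind could hide a real benefit or produce an apparent harm. The secondary outcome of drug-free weeks is built the same way and would share the error.

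**Working it through.** **1. Inputs (Protocol 11.4).** The design has "80% power using an alpha level of 0.05 (two-sided) and a 1:1 randomization ratio". For TAU, "we assumed a probability of 0.6 for stimulant-free urines in the TAU group". The difference is to be detected "if the probability of stimulant-free urines in the TAU+SCT group is at least 0.7". The correlation structure is compound symmetry with "a maximum correlation between any 2 time points of 0.65". The result is "The sample size yielded from the assumptions outlined above is 528, with 264 in each treatment group". Both rates are stated for urines. I treat them as weekly rates, since the week is the unit of the primary outcome.

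**2. Reproducing 528.** Comparing 0.60 with 0.70 at a single time point needs 356 per arm (pooled variance), or 376 with continuity correction. With m repeated measures, multiply by (1 + (m−1)×0.65)/m.
- m = 10: the factor is 0.685. Then 356×0.685 rounds up to 244 per arm, total 488. With continuity correction, 376×0.685 rounds up to 258, total 516.
- m = 7: the factor is 0.700. With continuity correction, 376×0.700 rounds up to 264, total 528.
- m = 4: the factor is 0.7375. Then 356×0.7375 rounds up to 263, total 526.

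The stated figure is reproducible. Section 11.4 does not give m or the formula variant, so the exact route is not identified.

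**3. Effect of false positives on the level comparison.** Let f be the fraction of truly stimulant-free TAU+SCT weeks scored positive because of cross-reaction. The documents give no value, so f is an assumption shown over a range. The observed TAU+SCT rate is 0.70(1−f), and the remaining difference is 0.70(1−f) − 0.60 = 0.10 − 0.70f.

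Power is from a logit-scale Wald test with 264 per arm and m = 10. At f = 0 the log odds ratio is 0.442 and its standard error is √[(0.685/264)(1/0.24 + 1/0.21)] = 0.152. The ratio is 2.90, and 2.90 − 1.96 = 0.94 gives 83%. The last column takes a true rate of 0.60 in both arms and gives the chance of a significant result against TAU+SCT.

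| f per week (assumed) | Observed TAU+SCT | Remaining difference | Power | False finding against TAU+SCT if no true effect |
|---|---|---|---|---|
| 0 | 0.700 | 10.0 points | 83% | 2.5% |
| 2% | 0.686 | 8.6 points | 70% | 5% |
| 5% | 0.665 | 6.5 points | 46% | 13% |
| 10% | 0.630 | 3.0 points | 13% | 39% |

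The difference reaches zero at f = 0.10/0.70 = 14.3% per week. If the two weekly samples err independently, that corresponds to 1 − √(0.60/0.70) = 7.4% per sample.

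**4. Incomplete exposure.** If only a share e of those weeks is exposed to bupropion, the loss is 0.70×e×f. Section 4.2.1 cites about 79% and 85% of doses taken in two earlier bupropion SR trials. Using these only as an illustration of e, at f = 5% the loss is 0.70×0.79×0.05 = 2.8 points or 0.70×0.85×0.05 = 3.0 points, instead of 3.5.

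**5. Effect on the slope.** Section 11.3.1 addresses the intervention effect through the treatment-by-week interaction. A constant f from week 1 lowers the whole curve and changes its slope little. As an assumed example, a rise from 0.60 to 0.75 is a logit change of 1.099 − 0.405 = 0.69. At f = 5% it becomes a rise from 0.570 to 0.7125, a logit change of 0.908 − 0.282 = 0.63.

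**The case against.** The strongest objection is that the decisive premise is not in the documents. No product, cut-off, specificity or false-positive rate is given, and structural kinship in section 8.1 does not show that an assay reacts. This stands. A reader might infer that the primary comparison is biased against TAU+SCT; the protocol does not support that, only a conditional risk of unknown size.

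Four further points also stand in part:
- Counting the amphetamine strip as a stimulant is the natural reading of 11.3.1, but it is an inference.
- A reader might infer that the error can arise in one arm only. Section 6.7.2 allows outside smoking treatment in TAU, so the contrast could be diluted. It would not be equal to an arm in which everyone is supplied with the drug.
- The percentage-point losses do not describe bias in the interaction term. They do describe the comparison stated in the primary hypothesis (11.1.1) and used for the sample size (11.4).
- Partial cross-checks exist. Self-reported stimulant-use days cannot be altered by the assay, and the week 16 and 28 urines fall well after the 3-day bupropion taper. These could raise suspicion of an artefact but would not correct the primary result.

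The objection that strip-level scoring can be left to a statistical analysis plan carries less weight. The protocol itself fixes the week rule in 11.3.1 and Table 6, and that fixed rule is what is at issue.

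**Conclusion.** The point holds in conditional form. The fixed rule, the separate amphetamine result and the one-arm supply of bupropion mean that any cross-reaction would count against TAU+SCT. Whether it occurs, and how often, cannot be settled from the protocol. Over the assumed range of f from 2% to 10%, the planned 10-point difference would fall to between 8.6 and 3.0 points, and about 14% would remove it. These losses are an upper bound at each f, because they assume full bupropion exposure. They rest on the planned rates of 0.60 and 0.70 and apply mainly to the level comparison.

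A reader might go further and conclude that any TAU+SCT disadvantage seen only under the stated scoring should be set aside as artefact. That does not follow: such a disadvantage could also reflect real, unreported amphetamine use. The safeguard must therefore be symmetric.

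**What to change.** 1. Keep the stated scoring as primary, and state in 11.3.1 and Table 6 which strips count as stimulants.
2. Pre-specify a sensitivity analysis, applied identically to both arms. In it, a urine positive on amphetamine alone (cocaine and methamphetamine negative, no self-reported stimulant use) does not make the week positive.
3. Report amphetamine-only positives by arm, and at baseline versus on treatment.
4. State that a conclusion in either direction that depends on the choice of scoring will be described as not robust.

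The cost is some wording and one re-run of the primary model. The panel lists amphetamine separately, so no new visits, samples or participants are needed. The drawback is that unreported use of amphetamine alone is missed in the second scoring, which is why it should not replace the primary one. The second scoring also cannot remove a false positive that appears on the methamphetamine strip as well.

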10.0 CONTINGENCY MANAGEMENT (CM)

The CM procedure utilized in early research typically followed the reinforcement schedule developed by Higgins et al. (1994) in which participants received vouchers for goods/services of escalating value based on maintaining a target behavior (e.g., drug-free urines, treatment attendance, etc.). While highly effective, this voucher-based procedure has been criticized as being more costly than most CTPs can afford, which led to the development of an intermittent reinforcement approach in which participants earn chances to draw for prizes based on maintaining a target behavior (Petry et al., 2000). This prize-based approach has been found to be effective in a number of studies, including a CTN study, CTN-0006, in which it was found to significantly increase treatment retention and negative urine drug screens in stimulant abusers (Petry et al., 2005).

In the present study, prize-based CM will be used to reinforce negative CO (i.e., CO < 4 ppm) results during the post-quit phase. The CO cut-off of < 4 ppm is consistent with research findings that the use of 2-3 ppm produces the most accurate identification of smoking abstinence whereas 8-10 ppm, which has been traditionally used to verify abstinence, can result in smokers being classified as abstinent (Javors et al., 2005; Cropsey et al., 2006). Participants can begin to earn abstinence incentives at the level of the study week whenever they submit a qualifying sample; this will encourage late quitters to continue to try to quit smoking throughout the active treatment phase. As outlined in Table 5, participants who start abstaining at week 4 and continue to abstain will receive a bonus draw for each negative CO sample starting in week 5. The number of draws will be reset to 4 whenever a participant submits a sample that indicates smoke exposure or if they have an unexcused missing CO sample. After two consecutive negative CO samples are again submitted, the third consecutive qualifying sample will reinstate the participant to receiving the number of draws associated with that study week. The bonus draw for achieving abstinence at week 4 will not be reinstated post-lapse. The maximum number of draws that can be earned is 110.

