11.3.4 Missing Data

Logistic regression analyses will be conducted to identify patterns of attrition and to determine if there is differential attrition by treatment condition. A binary indicator variable for missing data will be regressed on treatment assignment and other covariates. Variables that are associated with attrition at or below the α =0.10 level of significance will be included in subsequent analyses where the assumption of data missing at random (conditional on covariates) is required.

For the primary outcome measure, whether (yes/no) a participant is stimulant-free during each week of the active treatment phase, missing data will be addressed as described in section 11.3.1. For the smoking outcome measures, missing smoking self-report/CO data will be treated as positive for smoking.

For all other outcome measures, and as a supplementary sensitivity analysis for the outcome measures above, a model to predict the existence of missing data based on the baseline covariates will be examined. Any baseline covariate that is related to the occurrence of missing data will be added to the list of control covariates for the hypothesis test. To minimize any impact of attrition on the test of hypotheses, intent-to-treat analyses will be conducted for all hypotheses. The GLMM analysis described in section 11.3.1 allows a missing at random assumption (Dang, Mazumdar and Houck, 2008). With these methods, if data are MAR, weeks with missing outcome may be ignored, and will therefore not be imputed. If the random effects model (GLMM) unexpectedly fails to converge, a general estimating equation (GEE) approach treating site as a fixed effect will be used. If this model is utilized, then missing data will be multiply imputed using standard multiple imputation procedures, since GEE inference is only valid if data are missing completely at random (MCAR).

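### Table 6 lets a week without urine be scored positive or missing but never stimulant-free, which breaks the primary model's missing-at-random condition, and no stated sensitivity analysis departs from that condition

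*Protocol*

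**What the plan says.** **Coding of the week (protocol 11.3.1 and Table 6).** With no urine, "data for a week in which both urine samples are missing and the participant self-reports no illicit stimulant use will be treated as missing". Table 6 gives the whole row: positive if the TLFB has at least one use day, and missing if the TLFB is all negative, partly missing or wholly missing. With one negative urine and the other sample missing, the week is stimulant-free if use is denied, "or the self-report data are missing will be treated as negative"; a TLFB use day makes it positive. Section 6.5.2.1 carries the same handling over to drug-free weeks.

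**Missing weeks (11.3.1 and 11.3.4).** Section 11.3.1 states that inference from the mixed model requires MAR. Section 11.3.4 adds that "if data are MAR, weeks with missing outcome may be ignored, and will therefore not be imputed". Attrition is examined by logistic regression, and associated variables enter later models. The supplementary sensitivity analysis adds baseline covariates that predict missingness. Multiple imputation appears only as a fallback, with GEE, if the mixed model does not converge.

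**Incentives.** Table 3 (7.7) pays for visits and valid samples without restriction by arm, and 7.4 schedules both arms twice weekly. Only TAU+SCT has prize draws (10.0), in weeks 4-10, for CO below 4 ppm. The draws are reset after a sample that indicates smoke exposure "or if they have an unexcused missing CO sample".

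**The concern.** Take two participants who give no urine in a week. One used stimulants and says so on the TLFB; the week enters the analysis as positive. The other did not use and says so; the week is dropped. Among no-urine weeks, only admitted use is ever seen. That is dependence of missingness on the current outcome, and neither baseline covariates nor treatment in the model can remove it.

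The cell is likely to be filled. The TLFB is meant to cover every study day (6.5.2.1), so a missed week can be reconstructed at a later visit. Participants who stop early are asked back in week 10 for the Table 2 procedures, which include the TLFB (7.6.1).

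If no-urine rates differ between arms, part of that difference passes into the primary contrast. The stated sensitivity analysis shares the main analysis's assumption, so it cannot show whether the conclusion survives its failure.

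**Working it through.** **Inputs from protocol 11.4.** "The minimum sample size required to achieve 80% power using an alpha level of 0.05 (two-sided) and a 1:1 randomization ratio"; "a maximum correlation between any 2 time points of 0.65" under compound symmetry; "we assumed a probability of 0.6 for stimulant-free urines in the TAU group"; and an effect to be detected if "the probability of stimulant-free urines in the TAU+SCT group is at least 0.7". The stated size is 528, or 264 per arm. Section 7.4 gives 10 weeks.

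**The plan's own figure.** Two proportions, 0.6 against 0.7, need 356 per arm, or 376 with continuity correction. The repeated-measures factor is [1 + (m - 1) x 0.65]/m, which is 0.685 at m = 10 weeks.
- Without correction: 356 x 0.685 gives 244 per arm, 488 in total.
- With correction: 376 x 0.685 gives 258 per arm, 516 in total, within 3% of 528.
- With correction and m = 7 (factor 0.70): 264 per arm, exactly 528.

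The protocol states neither m nor the correction. I use 264 per arm and 0.685 below, only to scale the standard error.

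**Why MAR fails.** Let a be the share of use in no-urine weeks that is admitted on the TLFB. A stimulant-free week is observed with probability 1 - P(no urine | free). A use week is observed with probability 1 - P(no urine | use) x (1 - a). If giving urine is unrelated to use and 20% of weeks have none, the two are 0.80 and, at a = 0.5, 0.90. They are equal only at a = 0 or, where use and urine-giving are related, by a coincidental cancellation.

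**Size.** The documents give no no-urine rate, no use rate in such weeks and no admission rate, so all three are assumptions. Let m now be the no-urine share, u the use rate in those weeks, and 0.60 the true stimulant-free rate in both arms (no effect):

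observed rate = [0.60 - m(1 - u)] / [(1 - m) + m x u x a]

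Example with u = 0.4 and a = 0.5: TAU+SCT (m = 0.20) gives 0.48/0.84 = 0.571; TAU (m = 0.30) gives 0.42/0.76 = 0.553; difference +1.9 points.

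| u | a | TAU+SCT (m = 0.20) | TAU (m = 0.30) | Difference, points | Two-sided rejection |
|---|---|---|---|---|---|
| 0.4 | 0 | 0.600 | 0.600 | 0.0 | 5.0% |
| 0.4 | 0.5 | 0.571 | 0.553 | +1.9 | 8.2% |
| 0.4 | 1 | 0.545 | 0.512 | +3.3 | 15.2% |
| 0.6 | 0 | 0.650 | 0.686 | -3.6 | 18.4% |
| 0.6 | 0.5 | 0.605 | 0.608 | -0.3 | 5.1% |
| 0.6 | 1 | 0.565 | 0.545 | +2.0 | 8.6% |
| 0.8 | 0 | 0.700 | 0.771 | -7.1 | 61.6% |
| 0.8 | 0.5 | 0.636 | 0.659 | -2.2 | 9.9% |
| 0.8 | 1 | 0.583 | 0.574 | +0.9 | 5.7% |

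Rejection is a normal approximation with 264/0.685 = 385 effective participants per arm. It ignores information lost with dropped weeks and gives the model no credit for a participant's other weeks.

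Swapping the no-urine rates reverses every sign. With 20% in both arms and equal u and a, the level moves (0.571 in both arms at u = 0.4, a = 0.5), but the difference is zero and rejection stays at 5%.

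With a true effect of 0.7 against 0.6 and the same no-urine rates, the expected difference ranges from 2.9 points (0.800 against 0.771: use in no-urine weeks 40 points above each arm's average, none admitted) to 13.9 points (0.651 against 0.512: use at the average, all admitted).

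**One-urine weeks.** Apply the 0.65 within a week (an assumption). Two negatives then have probability 0.6² + 0.65 x 0.6 x 0.4 = 0.516, against 0.60 for one, a gap of 8.4 points. If the TLFB catches an assumed 80% of the missed use, 8.4 x 0.2 = 1.7 points remain. An assumed 20-point arm difference in second-sample completeness then moves the contrast by 1.7 x 0.2 = 0.3 points.

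**The case against.** **Incentives.** A reader might infer that only one arm is paid to attend. Table 3 contradicts this: both arms can receive up to 225 + 150 + 50 = $425 in the active phase. The prizes (up to about $380) reward a negative CO reading, not attendance, and the reset matters chiefly to those already abstaining from smoking. This objection stands. What remains is an unequal incentive, not payment of one arm only.

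**Cause.** A reader might also infer that MAR fails because attendance differs by arm. It does not, because treatment is in the model. The outcome dependence comes from the coding.

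**Direction.** It is tempting to say that the rule favours TAU+SCT. The documents do not fix the sign. Section 6.5.2.1 reports that an earlier trial saw lower treatment attendance in the smoking-cessation arm at non-methadone sites, although that concerns clinic sessions, not research visits. The table above shows both signs even for one fixed pair of no-urine rates.

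**The rule may help.** Counting admitted use as positive retains real information. If absent weeks are mostly use weeks, it offsets part of the bias from dropping them: at u = 0.8 the difference goes from -7.1 to -2.2 to +0.9 points as admission rises. This stands, and is a reason to keep the primary rule.

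**Other checks.** The attrition regression, the comparison of missing observations by arm (11.5) and the separate TLFB analysis of use days (11.3.2) would reveal an imbalance. They would not test its effect on the primary contrast.

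**Scope.** Sensitivity analyses are often left to a statistical analysis plan, which is not among the documents reviewed. Here, however, the protocol itself fixes the coding, the reliance on MAR and a sensitivity analysis within MAR.

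**Conclusion.** The point holds on the text: Table 6 makes observation of a no-urine week depend on its outcome, against the condition that the protocol sets for its own primary model, and nothing stated departs from MAR.

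The size is illustrative. With no true effect and assumed no-urine rates of 20% and 30%, the spurious difference lies between about -7 and +3 points, against a 10-point design effect. The two ends have different sources. The +3.3 comes from the coding alone, with urine-giving unrelated to use. The -7.1 arises with no use admitted, when the coding asymmetry is inactive and the fault is an untested MAR assumption. Equal no-urine, use and admission rates across arms give no spurious difference, only a shift in level.

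The one-urine rule is a minor matter, about 0.3 points under the assumptions shown. A figure of 1.7 points (8.4 x 0.2) would ignore the TLFB, which Table 6 lets override a single negative urine.

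**What to change.** Keep the primary rule. In section 11.3.4, replace or supplement the MAR-only sensitivity analysis for the primary outcome with:

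- **(a) Symmetric recoding with delta adjustment.** Set every no-urine week to missing whatever the TLFB says. Then use multiple imputation with arm-specific delta shifts, in both directions, to the tipping point, and report whether the shifts needed to change the conclusion are plausible.
- **(b) Missing-as-positive, as one bound only.** It should not be a condition for claiming an effect, because it turns attendance into outcome. With 0.60 stimulant-free everywhere and no-urine rates of 20% and 30%, it yields 0.60 x 0.80 = 0.48 against 0.60 x 0.70 = 0.42: a spurious 6 points, with rejection of about 39%.

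A sample-level urine analysis is optional, given the small one-urine effect.

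Cost: extra analysis on data already collected, with no added visits or measurements. The conclusion may prove less robust than the primary analysis alone suggests.
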